11. **Blood Chemistry:** Full chemistry panel (required tests are listed in [Table 8](#)) is required as follows: at Screening, Day 1 of Lead-in PK Period (if not performed in prior 3 days), Cycle 1 Day 1, Cycle 2 Day 1, Cycle 4 Day 1, Cycle 7 Day 1, then every 6 weeks thereafter. Core chemistry panel (required tests are listed in [Table 8](#)) is required as follows: on Cycle 1 Day 8, Cycle 2 Day 8, Cycle 3 Day 1, Cycle 5 Day 1, Cycle 6 Day 1, Cycle 8 Day 1, then every 2 weeks thereafter. If full and core chemistry panels are scheduled at the same visit, only the full chemistry panel will be performed. After amendment #4 approval, required every 6 weeks. Required tests are listed in [Table 8](#).
12. **Thyroid Function Tests:** free T4 and TSH will be performed at Screening, Lead-in Day 1 (only if not performed in prior 3 days), Cycle 4 Day 1, Cycle 7 Day 1, and Cycle 13 Day 1, and then Q12W thereafter. Additional tests should be performed when clinically indicated. Hypothyroidism should be treated per standard medical practice to maintain euthyroid state. See [Table 8](#).
13. **ACTH:** ACTH tests will be performed at Screening, Cycle 6 Day 1, then Q12W thereafter. Additional tests should be performed when clinically indicated. See [Table 8](#).
14. **Serum/Urine Pregnancy Test:** For female patients of childbearing potential, a serum pregnancy test, with sensitivity of at least 25 mIU/mL, will be performed at up to three occasions prior to starting combination study treatment: once at the start of screening, once at Lead-in Day 1 immediately before axitinib administration, and at the Cycle 1 Day 1 visit immediately before the administration of avelumab in combination with axitinib. Additional pregnancy tests (serum or urine) will also be routinely repeated at every treatment cycle during the active treatment period and additionally whenever one menstrual cycle is missed or when potential pregnancy is otherwise suspected. Additional pregnancy tests may also be undertaken if requested by Institutional Review Board (IRB)/Ethics Committees (ECs) or if required by local regulations (see [Section 7.1.1](#)).

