10. Blood Chemistry: Full chemistry panel (required tests are listed in Table 8) is required as follows: at Screening, Cycle 1 Day 1, Cycle 2 Day 1, Cycle 4 Day 1, Cycle 7 Day 1, then every 6 weeks thereafter. Core chemistry panel (required tests are listed in Table 8) is required as follows: Cycle 1 Day 8, Cycle 3 Day 1, Cycle 5 Day 1, Cycle 6 Day 1, Cycle 8 Day 1, then every 2 weeks thereafter. If full and core chemistry panels are scheduled at the same visit, only the full chemistry panel will be performed. After amendment #4 approval required every 6 weeks. Required tests are listed in Table 8.
11. Thyroid Function Tests: Free T4 and TSH will be performed at Screening, Cycle 4 Day 1, Cycle 7 Day 1, and Cycle 13, Day 1, and then Q12W thereafter. Additional tests should be performed when clinically indicated. Hypothyroidism should be treated per standard medical practice to maintain euthyroid state. See Table 8.
12. ACTH: ACTH tests will be performed at Screening, Cycle 6 Day 1, then Q12W thereafter. Additional tests should be performed when clinically indicated. See Table 8.
13. Serum/Urine Pregnancy Test: For female patients of childbearing potential, a serum pregnancy test, with sensitivity of at least 25 mIU/mL, will be performed at two occasions prior to starting combination study treatment: once at the start of screening and at the Cycle 1 Day 1 visit immediately before the administration of avelumab in combination with axitinib. Additional pregnancy tests (serum or urine) will also be routinely repeated at every treatment cycle during the active treatment period, and additionally whenever one menstrual cycle is missed or when potential pregnancy is otherwise suspected. Additional pregnancy tests may also be undertaken if requested by Institutional Review Boards (IRB)/Ethics Committees (ECs) or if required by local regulations (see Section 7.1.1).
14. Urinalysis: Required at Screening, at Cycle 1 Day 1 and then at Day 1 of every odd cycle and at the End of Treatment. After amendment #4 approval required every 12 weeks. If protein $\geq 2+$ by semiquantitative method (eg, urine dipstick), protein will have to be quantified by 24-hour urine collection. To be performed as clinically indicated at other time points. See Table 8.

090177e1907c3de00.1\Draft\Versioned On:01-Mar-2019 17:22 (GMT)

090177e1907c3de0\0.1\Draft\Versioned On:01-Mar-2019 17:22 (GMT)

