7.1.3. Laboratory Safety Assessments

Haematology, blood chemistry, and urinalysis will be collected at the time points described in the [Schedule of Activities](#) table and analyzed at local laboratories. They may also be performed when clinically indicated. The required laboratory tests are listed in [Table 8](#). Clinically significant abnormal laboratory results should be repeated as soon as possible (preferably within 24-48 hours) and followed up as per standard clinical practice unless otherwise specified in this protocol.

If a full and core chemistry panel are scheduled at the same visit, then only the full chemistry panel will be performed.

Table 8. Required Laboratory Tests

Hematology	Chemistry Panel (* denotes core chemistry test)	After amendment #4 approval Chemistry Panel (# denotes test to be performed only when clinically indicated)	Urinalysis	Coagulation Tests	Pregnancy Tests
Hemoglobin	ALT*	ALT	Protein, glucose, blood. Urine dipstick/other semiquantitative method, for urine protein: if $\geq 2+$, collect 24-hour	PT, INR PTT or aPTT	For female patients of childbearing potential, serum or urine
Platelets	AST*	AST			
WBC	Alkaline Phosphatase*	Alkaline Phosphatase			
Absolute Neutrophils	Sodium*	Sodium			
Absolute Lymphocytes	Potassium*	Potassium			
Absolute Monocytes	Magnesium*	Magnesium			
Absolute Eosinophils	Chloride*	Chloride			
Absolute Basophils	Total Calcium*	Total Calcium			
	Total Bilirubin* °	Total Bilirubin °			
	BUN or Urea*	BUN or Urea			
	Creatinine*	Creatinine			
	Glucose (non-fasted)*	Glucose (non-fasted)			
	Phosphorus or Phosphate*	Phosphorus or Phosphate			
	Albumin	Albumin [#]			
	Total Protein	Total Protein [#]			
	Uric Acid	Uric Acid [#]			
	Amylase	Amylase			
	Gamma glutamyl transferase (GGT)	Gamma glutamyl transferase (GGT)			
	Cholesterol	Cholesterol [#]			
	Creatine kinase	Creatine kinase			
	C-reactive protein (CRP)	C-reactive protein (CRP) [#]			
	Lactate dehydrogenase (LDH)	-			
	Lipase	Lipase			
	Triglycerides	Triglycerides [#]			
	Other tests: HBV, HCV				
	Thyroid Function Tests: TSH, free T4				

090177e1907c3de0\0.1\Draft\Versioned On:01-Mar-2019 17:22 (GMT)

	Other Tests: ACTH			
--	-----------------------------	--	--	--

° For potential Hy's Law cases, in addition to repeating AST and ALT, laboratory tests should include albumin, creatine kinase, total bilirubin, direct and indirect bilirubin, gamma glutamyl transferase, prothrombin time (PT)/INR, alkaline phosphatase.

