  - derived absolute count  $\geq 800/\text{mm}^3$
- Neutrophil count decreased
  - derived absolute count does not meet Grade 2-4 criteria, and
  - % value < % LLN value, and
  - derived absolute count  $\geq 1500/\text{mm}^3$

For **calcium**, CTCAE grading is based on Corrected Calcium and Ionized Calcium (CALCIO). Corrected Calcium is calculated from Albumin and Calcium as follows

Corrected Calcium (mmol/L) = measured total Calcium (mmol/L) + 0.02 (40 – serum Albumin [g/L]).

**Liver function tests:** Alanine aminotransferase (ALT), aspartate aminotransferase (AST), and total bilirubin (TBILI) are used to assess possible drug induced liver toxicity. The ratios of test result over upper limit of normal (ULN) will be calculated and classified for these three parameters during the on-treatment period.

Summary of liver function tests will include the following categories. The number and percentage of patients with each of the following during the on-treatment period will be summarized by treatment group:

- ALT  $\geq 3 \times \text{ULN}$ , ALT  $\geq 5 \times \text{ULN}$ , ALT  $\geq 10 \times \text{ULN}$ , ALT  $\geq 20 \times \text{ULN}$
- AST  $\geq 3 \times \text{ULN}$ , AST  $\geq 5 \times \text{ULN}$ , AST  $\geq 10 \times \text{ULN}$ , AST  $\geq 20 \times \text{ULN}$
- (ALT or AST)  $\geq 3 \times \text{ULN}$ , (ALT or AST)  $\geq 5 \times \text{ULN}$ , (ALT or AST)  $\geq 10 \times \text{ULN}$ , (ALT or AST)  $\geq 20 \times \text{ULN}$
- TBILI  $\geq 2 \times \text{ULN}$
- Concurrent ALT  $\geq 3 \times \text{ULN}$  and TBILI  $\geq 2 \times \text{ULN}$
- Concurrent AST  $\geq 3 \times \text{ULN}$  and TBILI  $\geq 2 \times \text{ULN}$
- Concurrent (ALT or AST)  $\geq 3 \times \text{ULN}$  and TBILI  $\geq 2 \times \text{ULN}$
- Concurrent (ALT or AST)  $\geq 3 \times \text{ULN}$  and TBILI  $\geq 2 \times \text{ULN}$  and ALP  $> 2 \times \text{ULN}$
- Concurrent (ALT or AST)  $\geq 3 \times \text{ULN}$  and TBILI  $\geq 2 \times \text{ULN}$  and (ALP  $\leq 2 \times \text{ULN}$  or missing)

Concurrent measurements are those occurring on the same date.

Categories will be cumulative, ie, a patient with an elevation of AST  $\geq 10 \times \text{ULN}$  will also appear in the categories  $\geq 5 \times \text{ULN}$  and  $\geq 3 \times \text{ULN}$ . Liver function elevation and possible Hy's Law cases will be summarized using frequency counts and percentages.

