### **Parameters with NCI-CTC grades available:**

The laboratory toxicities will be tabulated using descriptive statistics (number of patients and percentages) during the on-treatment period. The denominator to calculate percentages for each laboratory parameter is the number of patients evaluable for CTCAE grading (ie those patients for whom a Grade 0, 1, 2, 3 or 4 can be derived).

- The summary of laboratory parameters by CTCAE grade table will include number and percentage of patients with Grade 1, 2, 3, 4, Grade 3/4 and any grade (Grades 1-4), laboratory abnormalities during the on-treatment period.
- The shift table will summarize baseline CTCAE grade versus the worst on-treatment CTCAE grade. The highest CTCAE grade during the on-treatment period is considered as the worst grade for the summary.

The above analyses apply to hematology and chemistry evaluations which can be graded per CTCAE, ie:

- Hematology:

Hemoglobin (HB), Leukocytes (white blood cell decreased), Lymphocytes (lymphocyte count increased/decreased), Neutrophils / Absolute Neutrophils Count (ANC) (neutrophil count decreased), Platelet Count (PLT) (platelet count decreased).

- Serum Chemistry:

Albumin (hypoalbuminemia), Alkaline Phosphatase (alkaline phosphatase increased), Alanine Aminotransferase (ALT) (ALT increased), Amylase (serum amylase increased), Aspartate Aminotransferase (AST) (AST increased), Total Bilirubin (blood bilirubin increased), Cholesterol (cholesterol high), Creatinine (creatinine increased), Creatine Kinase (CPK increased), Potassium (hypokalemia/ hyperkalemia), Sodium (hyponatremia/ hypernatremia), Magnesium (hypomagnesemia/hpermagnesemia), Calcium (hypocalcemia/ hypercalcemia), Glucose (hypoglycemia/hyperglycemia), Gamma Glutamyl Transferase (GGT) (GGT increased), Lipase (lipase increased), Phosphates (hypophosphatemia), Triglycerides (hypertriglyceridemia).

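### Calcium is graded only on albumin-corrected or ionized values, yet calcium is often drawn without albumin, so worst calcium grades can be under-counted

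*SAP*

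**What the plan says.** **Grading rule.** SAP Section 6.6.5.1 states for calcium: "CTCAE grading is based on Corrected Calcium and Ionized Calcium (CALCIO). Corrected Calcium is calculated from Albumin and Calcium". The correction adds 0.02 mmol/L to total calcium for each g/L by which albumin lies below 40. No rule covers a calcium result that has neither an albumin nor an ionized value. SAP Section 5.3.1 analyses data as observed and imputes nothing unless a section says otherwise.

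**Tables affected.** Hypocalcemia and hypercalcemia are among the parameters in the CTCAE grade table and the baseline-to-worst shift table. For these, "The highest CTCAE grade during the on-treatment period is considered as the worst grade for the summary". The denominator is every patient for whom any grade can be derived. CTCAE-graded laboratory abnormalities are a secondary endpoint (Protocol Section 2.2, SAP Section 3.2.1).

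**What is drawn.** Protocol Table 8 (Section 7.1.3) heads its first chemistry column "Chemistry Panel (* denotes core chemistry test". The asterisk is on "Total Calcium" but not on albumin, and ionized calcium is not listed. The second column is headed "After amendment #4 approval Chemistry Panel (# denotes test to be performed only when clinically indicated"; there albumin carries the mark and total calcium does not.

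**When it is drawn.** The blood chemistry footnotes to the Schedule of Activities place the full panel at screening and then "Cycle 1 Day 1, Cycle 2 Day 1, Cycle 4 Day 1, Cycle 7 Day 1, then every 6 weeks thereafter". Dose-finding patients also have it at Lead-in Day 1 if it was not done in the prior 3 days. For the expansion phase, "Core chemistry panel (required tests are listed in Table 8) is required as follows: Cycle 1 Day 8, Cycle 3 Day 1", followed by Cycles 5, 6 and 8 and then every 2 weeks. Dose finding adds a core panel at Cycle 2 Day 8. After amendment #4, chemistry is required every 6 weeks.

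**The concern.** The grading rule needs two inputs, and the protocol by design omits one of them at core-panel visits and, after amendment #4, at every routine cycle visit. Applied as written, those calcium results get no grade.

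A worst grade is a maximum, so leaving results out can lower it but never raise it. A patient whose only abnormal calcium falls at a core-panel visit can appear as evaluable with Grade 0, because a paired draw at Cycle 2 Day 1 supplied a grade. Nothing in the table would show how many calcium samples went ungraded. After amendment #4, whether a result can be graded depends on whether someone chose to order albumin.

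If the programmer instead carries albumin forward or grades uncorrected calcium, the result rests on a choice that the SAP does not record. Elsewhere the SAP does plan for incomplete inputs: Section 6.6.5.1 derives absolute cell counts from percentages and says how a missing alkaline phosphatase is handled in the liver categories.

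**Working it through.** The plan states no figure on this point, so the check is a count of scheduled draws.

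**Inputs and assumptions**
- The schedules come from the blood chemistry footnotes, and the panel contents from Table 8.
- In the expansion phase, Cycle 1 Day 1 is the pre-dose baseline and is not counted. In dose finding, study treatment starts with the axitinib lead-in (SAP Section 3.4.1), so Cycle 1 Day 1 is post-baseline and is counted.
- Corrected calcium is assumed to need albumin from the same visit.
- Share not gradable = (calcium draws − draws with albumin) / calcium draws.

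**Before amendment #4, through Cycle 13**
- Expansion: draws at C1D8 and Day 1 of C2 to C13, 1 + 12 = 13. Albumin at C2, C4, C7, C10 and C13, 5 draws. Not gradable: (13 − 5)/13 = 8/13 = 62%.
- Dose finding: draws at C1D8, C2D8 and Day 1 of C1 to C13, 2 + 13 = 15. Albumin at C1, C2, C4, C7, C10 and C13, 6 draws. Not gradable: (15 − 6)/15 = 9/15 = 60%.

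**Adding End of Treatment and Day 30**, both full panels:

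| Last cycle | Expansion, cycle draws only | Expansion, with both | Dose finding, cycle draws only | Dose finding, with both |
|---|---|---|---|---|
| 4 | 2/4 = 50% | 2/6 = 33% | 3/6 = 50% | 3/8 = 38% |
| 8 | 5/8 = 63% | 5/10 = 50% | 6/10 = 60% | 6/12 = 50% |
| 13 | 8/13 = 62% | 8/15 = 53% | 9/15 = 60% | 9/17 = 53% |
| 26 | 17/26 = 65% | 17/28 = 61% | 18/28 = 64% | 18/30 = 60% |

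From Cycle 7 on, one Day 1 draw in three has albumin, so the long-run share is 2/3.

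**After amendment #4.** No routine cycle draw includes albumin, so all of them are ungradable unless albumin is ordered for cause. The approval date is not in the documents. As an illustration only, for a patient treated for 78 cycles in expansion:
- approval at Cycle 13: 30/34 = 88%
- approval at Cycle 27: 35/44 = 80%
- approval at Cycle 40: 39/52 = 75%

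The dose-finding figures are 86%, 78% and 74%.

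**How long an abnormality must last to be seen before amendment #4.** On the expansion schedule through Cycle 13:
- One visit only: falls on an ungradable draw in 8 of 13 positions (62%).
- Two consecutive visits: both ungradable in 3 of 12 positions (C5–C6, C8–C9, C11–C12), 25%.
- Three consecutive visits: never entirely ungradable.

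**Size of the correction.** With albumin at 30 g/L, 0.02 × (40 − 30) = 0.2 mmol/L is added. An uncorrected value would be lower by that amount.

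**The case against.** **Same-visit albumin is an inference.** The SAP does not say which albumin goes with which calcium. Its same-date definition is given for concurrent liver tests, and Section 5.3.1 does not address pairing two observed values from different days. This stands. It turns the defect into an unstated pairing rule, which still needs to be written down.

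**Most patients remain gradable.** A reader might infer that the calcium table will be nearly empty, or that about 62% of abnormalities will be missed. Neither is supported. The percentages count scheduled results, not patients, and nearly every treated patient has a paired draw at Cycle 2, Cycle 4 or End of Treatment. The 62% applies only to an abnormality present at a single visit with no repeat. Protocol Section 7.1.3 asks for clinically significant abnormal results to be repeated, and SAP Section 5.2.9 keeps unscheduled results in everything except by-visit descriptive statistics. Such a repeat helps only if albumin or ionized calcium is measured with it.

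**Calcium is not hidden.** By-visit summaries, Low/Normal/High categories and flagged listings use the raw values. Abnormal tests that cause symptoms, further testing or intervention are reportable under Protocol Section 8.5. This stands and confines the problem to the derived grade and shift tables.

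**Risk groups.** A reader might infer that the MSKCC and Heng groups, which use corrected calcium, are compromised. They are baseline classifications, and screening has the full panel.

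**Weight.** This is one analyte in a descriptive Phase 1b study without hypothesis testing. The laboratory DLT criterion turns on medical intervention or hospitalization, not on this table.

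**Conclusion.** The conflict between SAP Section 6.6.5.1 and Protocol Table 8 is real. Before amendment #4, about 60% of scheduled on-treatment calcium results through Cycle 13 cannot be graded. The share is about 53% once the End of Treatment and Day 30 panels are counted, and half or less for patients stopping by about Cycle 8. After amendment #4, no routine cycle draw can be graded.

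The consequence is possible under-counting in the CTCAE grade and shift tables. Before amendment #4 this concerns transient abnormalities; after it, any later abnormality for which albumin was not ordered. The primary endpoint is not touched.

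The figures rest on same-visit pairing and no imputation. For-cause albumin or locally measured ionized calcium would narrow the gap by an unknown amount. It is unclear whether End of Treatment and follow-up panels keep albumin after amendment #4: their footnotes still call for full chemistry, while Table 8 marks albumin for cause. Day 30 results count only if they fall inside the on-treatment period, which ends 30 days after the last dose or earlier if new anti-cancer drug therapy starts. Without the approval date, the effect of amendment #4 on the 18-month primary analysis cannot be stated; patients on long treatment in the final analysis are the most exposed.

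**What to change.** In SAP Section 6.6.5.1, state that when same-day albumin is missing, calcium is corrected with the most recent earlier albumin and flagged. Report the number of calcium samples graded with same-day albumin, graded with carried-forward albumin, and not graded.

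Show any grading of uncorrected total calcium only as a separate, flagged sensitivity summary. It departs from the SAP's own basis, and low albumin biases it toward hypocalcemia and away from hypercalcemia.

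Reconcile Table 8 with the SAP on albumin, including at End of Treatment and follow-up after amendment #4. Hypoalbuminemia is also a graded parameter and has the same gap in collection.

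The cost is a few sentences in the SAP and a flag in the laboratory dataset. The SAP rule needs no new blood draws and can be applied to data already collected. The downside is that a carried-forward albumin makes the correction approximate, increasingly so long after amendment #4, when the last routine albumin may be old.

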### **Parameters with NCI-CTC grades available:**

The laboratory toxicities will be tabulated using descriptive statistics (number of patients and percentages) during the on-treatment period. The denominator to calculate percentages for each laboratory parameter is the number of patients evaluable for CTCAE grading (ie those patients for whom a Grade 0, 1, 2, 3 or 4 can be derived).

- The summary of laboratory parameters by CTCAE grade table will include number and percentage of patients with Grade 1, 2, 3, 4, Grade 3/4 and any grade (Grades 1-4), laboratory abnormalities during the on-treatment period.
- The shift table will summarize baseline CTCAE grade versus the worst on-treatment CTCAE grade. The highest CTCAE grade during the on-treatment period is considered as the worst grade for the summary.

The above analyses apply to hematology and chemistry evaluations which can be graded per CTCAE, ie:

- Hematology:

Hemoglobin (HB), Leukocytes (white blood cell decreased), Lymphocytes (lymphocyte count increased/decreased), Neutrophils / Absolute Neutrophils Count (ANC) (neutrophil count decreased), Platelet Count (PLT) (platelet count decreased).

- Serum Chemistry:

Albumin (hypoalbuminemia), Alkaline Phosphatase (alkaline phosphatase increased), Alanine Aminotransferase (ALT) (ALT increased), Amylase (serum amylase increased), Aspartate Aminotransferase (AST) (AST increased), Total Bilirubin (blood bilirubin increased), Cholesterol (cholesterol high), Creatinine (creatinine increased), Creatine Kinase (CPK increased), Potassium (hypokalemia/ hyperkalemia), Sodium (hyponatremia/ hypernatremia), Magnesium (hypomagnesemia/hpermagnesemia), Calcium (hypocalcemia/ hypercalcemia), Glucose (hypoglycemia/hyperglycemia), Gamma Glutamyl Transferase (GGT) (GGT increased), Lipase (lipase increased), Phosphates (hypophosphatemia), Triglycerides (hypertriglyceridemia).

### **Parameters with NCI-CTC grades not available:**

Hematology and chemistry evaluations which cannot be graded per CTCAE criteria will be summarized as frequency (number and percentage) of patients with:

- shifts from baseline normal to at least one result above normal during on-treatment period
- shifts from baseline normal to at least one result below normal during on-treatment period

In this study, these apply to the following parameters:

- Hematology: Absolute Monocytes, Absolute Eosinophils, Absolute Basophils

- Serum Chemistry: Chloride, Total Urea, Uric Acid, Total Protein, C-Reactive Protein, Lactate Dehydrogenase (LDH), TSH, Free T4, ACTH, ANA (performed at baseline and if clinically indicated), ANCA (performed at baseline and if clinically indicated), RF (performed at baseline and if clinically indicated), HBV and HCV (performed at baseline and if clinically indicated).

#### **6.6.5.2. Other laboratory parameters**

All other parameters collected on the eCRF will be listed in dedicated listings presenting all corresponding collected information on the eCRF.

- Coagulation: activated partial thromboplastin time (aPTT), prothrombin time (PT), international normalized ratio (INR), and PTT.
- Urinalysis: all urinalysis parameters, including protein, glucose, blood and albumin
- Other parameters: hormone, and immunology parameters
- Pregnancy test

The listings of laboratory results will be provided for all laboratory parameters. The listings will be sorted by parameters and assessment dates or visits for each patient. Laboratory values that are outside the normal range will also be flagged in the data listings, along with corresponding normal ranges. A listing of CTCAE grading will also be generated for those laboratory tests.

In addition, listings of abnormal values will be provided for hematology, chemistry, urinalysis, coagulation parameters. If there is at least one abnormal assessment for any parameter, all the data for that laboratory parameter will be included into the listing.

For all tests not mentioned above but present in the clinical data, a listing of patients with at least one result for the relevant test will be provided.

